11.3. Compensation for Participants

No compensation is provided for patients in this study.

11.4. Legal obligations

11.4.1. Roles of the Sponsor

The CMC Ambroise Paré is the sponsor of this research and is responsible for its conduct. The sponsor reserves the right to discontinue the research at any time for medical or administrative reasons; except in cases of force majeure, the investigator's opinion on this decision will be obtained and recorded in the trial documentation.

11.4.2. Approval of the protocol and amendments

Prior to the start of the study, the protocol, the information sheet, the informed consent form, and any other relevant documents will be submitted to the Institutional Review Board (IRB) for review. Notification of the HPC's favorable opinion will be forwarded to the study sponsor. This document must include a list of the HPC members who were present on the day the opinion was issued, along with their positions and qualifications.

The sponsor will notify the French National Agency for Medicines and Health Products Safety (ANSM) of the study.

The study may only be initiated after the sponsor has received all documents required from an ethical and regulatory standpoint, and in particular the favorable opinion of the CPP.

Any substantial modification to the protocol concerning the study's objectives, design, study population, or significant administrative aspects will require the approval of the coordinating investigator and the sponsor, as well as a favorable opinion from the CPP.

11.4.3. Commitment to Compliance with "Reference Methodology" MR-001

This study falls within the scope of the CNIL's Reference Methodology MR-001 for the following reasons:

- the collection of health data for research purposes
- obtaining the opinion of an IRB prior to commencing the research
- the use of anonymized data (identified by the inclusion number)
- providing information and obtaining individual consent from the participants
- access to data limited to healthcare and research professionals involved in the study under the responsibility of the investigators or the sponsor.

The Ambroise Paré Clinical Research Center, the study sponsor, has signed a commitment to comply with the "Reference Methodology" MR-001.

Patient data confidentiality will be ensured by using enrollment numbers and initials on the documents required for the research, or by appropriately redacting personally identifiable information from copies of source documents needed for research documentation. Only coded data will be accessible to the Sponsor.

The identity of participants will not be disclosed in any report or publication resulting from this study.

In accordance with the Law of March 4, 2004, on patients' rights, and if they so request of their investigator, participants in this study may be informed of the study's results once it has been completed.

11.4.4. Final Research Report

The final research report is prepared and signed by the sponsor and the coordinating investigator. A summary of the report, drafted in accordance with the Competent Authority's reference template, must be submitted to the Competent Authority and to the CPP within one year of the end of the research, corresponding to the end of the participation of the last person enrolled in the study.

12. DATA PROCESSING AND RETENTION OF DOCUMENTS AND DATA RELATED TO THE RESEARCH

12.1. Electronic Case Report Form (eCRF)

All information required by the protocol will be recorded in an electronic case report form (eCRF), with data hosted on a central, secure server at the CMC Ambroise Paré. Data will be collected as it is obtained by the investigator and/or personnel designated by the investigator.

12.2. Data Entry and Processing

The data required to conduct the study are listed in the table below, which specifies, for each document, its format, processing, and content.

	Format	Processing	Content
Consent form	Paper	Document completed by the patient and filed: - by the investigator's site in a secure location.	It contains proof of the patient's information and consent.
Inclusion form	Digital	Document completed by the site and used to notify the sponsor of a new patient's inclusion in the study.	This form contains the but not the patient's identity.
List of included patients	Paper	Confidential document retained by each investigator.	Document containing identifying data available only to the investigator; it allows the patient to be contacted if necessary. It also allows the study-specific enrollment number to be linked to the patient's medical record
Data collected by the investigator	Electronic	e-CRF	This data does not contain any information that would allow identify the patient.

12.3. Archiving

In accordance with the decree of August 11, 2008, establishing the retention period for documents and data related to biomedical research other than that involving medicinal products for human use, to be maintained by the sponsor and the investigator, upon completion of the research:

- all documents (various versions of the protocol, case report forms, investigator's file, consent forms, correspondence, etc.) in paper form will be archived at the center and at the sponsor's premises for 15 years.
- Data in electronic format will be retained until the final research report is completed and then archived for 15 years.

12.4. Ownership of Data

The CMC Ambroise Paré is the owner of the data, and no use or transfer to a third party may be made without its prior written consent.

12.5. Identification of all data to be collected in the observation log

Preoperative data:

- Age
- Gender
- Height
- Weight
- Medical history
- Data on first implantation

Intraoperative data:

- Result of probe parameter test
- Defibrillation circuit test result
- ICD impedance
- Any complications

Postoperative data:

- Results of the lead parameter test

13.FINANCING AND INSURANCE

13.1. Study funding

The costs associated with conducting this research are the responsibility of the sponsor.

13.2. Insurance

The Sponsor has taken out insurance for the entire duration of the study (under policy number BARCLT18496 with Lloyd's) covering its own civil liability as well as that of the investigators responsible for directing and supervising the conduct of the study on behalf of the Insured, and of any other party involved in this study on behalf of the Insured. This insurance policy, in accordance with Article L.1121-10 of the Public Health Code, is taken out with **Lloyd's**, [name].

14. PUBLICATION RULES

The study will be registered on the ClinicalTrials.gov website.

This study will be published in the form of presentations and original articles. The order of authorship will be determined by [name] [name], the principal investigator.

The CMC Ambroise Paré must be cited as the sponsor of the research and as a source of funding, if applicable.

16. APPENDICES

Appendix 1: Defibrillation circuit testing using synchronized high-energy shocks by manufacturer.

APPENDIX 1: TEST OF THE SYNCHRONOUS HIGH-ENERGY SHOCK DEFIBRILLATION CIRCUIT BY MANUFACTURER.

AED	Defibrillation Circuit Test	Expected impedance value
MEDTRONIC	Delivery of a synchronized shock to a spontaneous QRS (cardioversion) at a maximum energy of 35 J. In the event of a circuit break, the ICD will protect itself and will not deliver a shock. In the case of a pacemaker-dependent patient, the ICD cannot perform cardioversion (no synchronization possible on a Vs), it must then choose a defibrillation at 35J.	< 150 Ω
SJM/ABBOTT	Delivery of a synchronized shock on a spontaneous QRS with a recommended energy of 36 J. Retrieval of the shock impedance by re-querying the defibrillator.	20–120 Ω
BIOTRONIK	Delivery of a manual R-wave shock at 40 J.	50–150 Ω
BOSTON SCIENTIFIC	Delivery of two synchronized shocks triggered by the R-wave. A first shock at 1.1 J, followed by a ^{second} verification shock at 41 J. Only the combination of these two tests can truly confirm the integrity of the system, particularly the leads.	15 – 120 Ω
MICROPORT	Delivery of a 42 J shock (maximum energy) Program therapies in advance, which allows the ICD, in the event of arrhythmia induction, to diagnose and treat the triggered arrhythmia.	30–60 Ω (dual-coil probe) 50–10 Ω (single-coil probe)

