4. EVALUATION CRITERIA

4.1. Primary endpoint

The primary endpoint is the intraoperative catheter failure rate based on an abnormal shock impedance value (as defined by the manufacturer in Appendix 1).

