5. SELECTION OF RESEARCH PARTICIPANTS

5.1. Inclusion Criteria

The following patients will be included:

- Over 18 years of age,
- Who have a VVI, DDD, or BiV defibrillator implanted and require a device replacement due to battery wear,
- Who have given their consent to participate in accordance with regulations,
- Currently enrolled in a social security program or eligible for coverage.

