6.2.2. In the operating room

The procedure will be performed under general anesthesia or sedation, at the physician's discretion.

a) Before replacing the defibrillator's housing

Testing the lead parameters on the old defibrillator case

b) Replacement of the defibrillator housing

Replacement of the defibrillator housing and visual inspection of the connectors, following standard procedure.

After replacing the defibrillator housing

- Testing of probe parameters before and after connection to the new housing.
- Testing the defibrillation circuit:

Either via the standard defibrillation test, which involves inducing a ventricular arrhythmia through electrical cardiac stimulation and verifying the quality of its detection and the effectiveness of defibrillation.

Or via a high-energy synchronized shock; the test involves delivering a high-energy electrical shock synchronized with the QRS complex, in accordance with each manufacturer's standard guidelines (Appendix 1).

Important points:

- The use of an electrosurgical unit during surgery must be specified by the investigator, as its use may increase the risk of damaging the probe.
- If a malfunction of the defibrillation lead is detected during surgery, it will be replaced during the same procedure.

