6.3. Study Design

Steps	Inclusion Visit	In the operating room	3 months post-procedure (± 3 months)	12 months post-surgery (± 3 months)
	Pre-procedure Pre-procedure cardiology visit			
Information	R			
Consent	R			
Verification of criteria inclusion and non-inclusion	R			
Testing the probe settings on the old housing		R		
Replacing the defibrillator		S		
Visual inspection of the connectors		S		
Testing the probe parameters before and after connecting to the new housing		S		
Testing the defibrillation circuit on the new unit		R		
Test of probe parameters at 3 months (± 3 months) and 12 months (± 3 months) post-procedure			S	S
Recording of any complications		S	S	S

R: Procedures, processes, and treatments added by the research;

S: Procedures, processes, and treatments related to care

6.4. Expected duration of participant involvement, description of the timeline and duration of the study

The study for a patient begins when the patient and the investigator sign the consent form and ends at the 12±3-month visit. For each patient, the duration of the study will therefore be 12 months (± 3 months).

The planned enrollment period is 24 months. The study is expected to take 39 months to complete, starting from the date of the first enrollment.

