8. STATISTICAL

8.1. Description of planned statistical methods

Study population

All included subjects will be included in the analyses, which will be conducted according to the ITT principle.

Statistical analyses

An initial analysis of the data will provide a description of the overall population. The normality of the distribution of quantitative variables will be assessed using the Shapiro-Wilks normality test. Statistical results will be presented as means \pm standard deviations for quantitative variables with a Gaussian distribution, and as medians and interquartile ranges for other variables. For qualitative variables, frequencies and associated percentages will be presented. Qualitative variables will be compared using a chi-square test. If the conditions for conducting this test are not met, Fisher's exact test will be used. Quantitative variables will be compared between the two groups: for normally distributed variables, using a Student's t-test or an analysis of variance; for non-normally distributed variables, using a Wilcoxon-Mann-Whitney test.

Analysis of the primary outcome measure

Dysfunction rates will be estimated as point estimates and 95% confidence intervals.

Analysis of Secondary Endpoints

Depending on the rates of dysfunction observed, logistic regression will be used to estimate the variables associated with the risk of dysfunction. If the rate is too low for such modeling, descriptive analyses will be performed.

Modeling of dysfunction times over time may be performed using a Kaplan-Meier model. A Cox regression may be adjusted to determine the associated variables.

8.2. Expected number of participants to be included in the study, with statistical justification

Since the primary objective is to detect a non-zero rate of probe malfunction at the time of the procedure, we base the calculation of the sample size on the binomial distribution and the probability of observing no malfunctions in a sample of size n . Assuming a minimum malfunction rate of 1%, a study of 299 subjects yields a probability of observing no malfunctions that is less than an alpha risk of 5%. To account for unusable data and withdrawals of consent, we propose including a total of $N=330$ subjects in this study.

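### As supplied, Appendix 1 gives an empty expected range (50–10 Ω) for Microport single-coil systems, so the primary endpoint has no usable upper limit for that group; check the source page and correct the cell if it prints this

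*Combined protocol and SAP*

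**What the plan says.** The primary endpoint (section 4.1) is the "intraoperative catheter failure rate based on an abnormal shock impedance value (as defined by the manufacturer in Appendix 1"). Appendix 1 is a table with one row per defibrillator manufacturer and a column of expected impedance values. The Microport row has two entries: "30–60 Ω (dual-coil probe") and "50–10 Ω (single-coil probe").

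Three other sections bear on how the table is used:

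- Section 5.1 admits any patient "Who have a VVI, DDD, or BiV defibrillator implanted and require a device replacement due to battery wear". It does not restrict the brand.
- The schedule in section 6.3 lists "Testing the defibrillation circuit on the new unit". The row that applies is therefore the one for the new generator.
- Section 6.2.2 says: "If a malfunction of the defibrillation lead is detected during surgery, it will be replaced during the same procedure". It gives no impedance limit of its own.

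No other section gives an expected range for a Microport generator with a single-coil lead.

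**The concern.** The Appendix 1 column is the event definition for the primary endpoint. One entry, read as a lower and an upper limit like its neighbours, cannot be satisfied by any reading. For patients in that cell the plan as supplied does not say which impedances are failures.

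The primary objective (section 3.1) is to show that the failure rate is not zero, and section 8.2 sizes the study on the chance of seeing no failures at all. In such a design single events matter. One wrongly scored failure in an otherwise event-free series would change the primary answer, and one missed failure could do the reverse. The study is multicentre (section 6.1), so different sites could fill the gap with different limits. If an operator used the table to decide whether a lead is malfunctioning, the gap could also bear on lead replacement.

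**Working it through.** **Sample size, reproduced first.** Section 8.2 uses a minimum rate of 1%, alpha of 5% and n = 299. The smallest n with 0.99^n < 0.05 is ln 0.05 / ln 0.99, rounded up, which is 299. As a check, 0.99^298 = 0.05004 and 0.99^299 = 0.04954. The plan's figure is right and does not depend on the Appendix 1 cell.

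**The range as supplied.** A normal reading x would need 50 ≤ x ≤ 10. No x meets this.

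**Comparison with the rest of the column.**

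| Row | Expected value (Ω) | Order |
|---|---|---|
| Medtronic | < 150 | upper limit only |
| SJM/Abbott | 20–120 | ascending |
| Biotronik | 50–150 | ascending |
| Boston Scientific | 15–120 | ascending |
| Microport, dual-coil | 30–60 | ascending |
| Microport, single-coil | 50–10 | descending |

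The other four two-sided ranges all ascend. The lower limits shown elsewhere are 15, 20, 30 and 50 Ω, so 10 Ω would be the lowest in the table if it were a lower limit. Both facts favour a lower limit of 50 Ω and a damaged upper limit.

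**What a lost digit leaves open (assumption: exactly one digit is missing from 10).** Adding one digit without a leading zero gives 100 to 109, then 110, 120 and so on to 190, then 210, 310 and so on to 910. The upper limit would be at least 100 Ω and is not otherwise fixed. Three candidates serve as illustrations: 100 Ω (a final zero lost), and 120 and 150 Ω (both upper limits in other rows).

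| Reading | 50–100 Ω | 50–120 Ω | 50–150 Ω |
|---|---|---|---|
| 40 Ω | abnormal | abnormal | abnormal |
| 70 Ω | normal | normal | normal |
| 110 Ω | abnormal | normal | normal |
| 130 Ω | abnormal | abnormal | normal |

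The three candidates agree on every reading up to 100 Ω and above 150 Ω. They can differ only for readings above 100 and up to 150 Ω.

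**Size per patient.** One changed classification moves the failure rate by 1/299 = 0.334 percentage points. At the 1% design floor the expected number of failures is 299 × 0.01 = 2.99, so one patient is about a third of that count. The brand and coil mix is not given, so the number of patients affected cannot be computed.

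**The case against.** The strongest objection is that this may not be an error in the plan. The finding rests on one cell of a table read from a PDF, and a digit can be lost in reading. That stands, and it is why the first step is to look at the page. It does not dispose of the point: the dash, unit and coil label are intact and there is no gap or redaction mark, so a printed error remains possible.

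Second, the plan points to the remedy. Section 4.1 says the limits are the manufacturer's, and section 6.2.2 has the synchronised shock follow each manufacturer's guidance. An operator who met an impossible range would probably look it up. This makes it unlikely that the empty range would be applied as written, but it does not ensure that all sites would adopt the same limit.

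Third, the effect on scoring is recoverable. Section 12.5 collects the circuit test result and the ICD impedance, so patients can be re-scored once the limit is known. That stands. Only a decision already taken in the operating room could not be undone, and section 6.2.2 does not tie lead replacement to the Appendix 1 limits.

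A reader might infer that reversed bounds, 10–50 Ω, are an equally good repair, so that readings such as 40 Ω and 70 Ω would be classified in opposite ways. The table does not support this: every other two-sided range ascends, and 10 Ω would be below every other lower limit. The realistic ambiguity is the upper limit alone.

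**Conclusion.** The point holds, on condition that the source page prints what the supplied text shows. In that case a limit on which the primary endpoint depends is unusable for Microport generators with single-coil leads. The practical consequence is an undefined upper limit and possible inconsistency between sites for readings above 100 Ω. The case for a missing digit rests on the pattern of the other rows; the documents do not state the correct value, and none is proposed here.

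The size is about 0.33 percentage points per changed classification at n = 299. The number of such patients is unknown and may be zero. The sample size of 299, and the 330 to be enrolled, are unaffected.

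A reader might infer that every Microport single-coil patient will in fact be counted as a failure, and that the failure rate will be inflated accordingly. The documents do not support that. It needs both literal use of an impossible range and a patient share that is nowhere given. Nor do they show that any lead would be replaced needlessly.

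**What to change.** 1. Check the Microport row on the source page of Appendix 1. If it shows a valid range, no change is needed.
2. If it prints 50–10 Ω, replace that cell with the range in the manufacturer's documentation and cite the source in the appendix.
3. Notify sites of the corrected range before they use the table again during surgery.
4. Re-classify any Microport-generator, single-coil patients already scored, using the recorded ICD impedance. This assumes that the recorded value is the shock impedance. Section 12.5 does not name generator make or coil type as separate items, so these may have to be taken from the implant record.

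The cost is one page check and, if the error is confirmed, one corrected cell, one notice to sites and a short re-scoring exercise. Test procedures and sample size do not change.
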